Approximately, 30 subjects with angina, no obstructive CAD, and CMD invasively diagnosed by abnormal coronary flow reserve (CFR) and/or hyperemic microvascular resistance (HMR) will be enrolled in this single arm study. The primary objective is to evaluate the effect of CS narrowing using the Neovasc Reducer™ System on CFR and HMR at 4 months post Reducer implantation. Additional data will be collected on the adverse events and procedural success of the Reducer implantation procedure; as well as 4-months post-implant symptomatic and quality of life improvement as measured by the Canadian Cardiovascular Society (CCS) angina class, Seattle Angina Questionnaire short acting nitrates consumption frequency, functional capacity, intracardiac filling pressures, and ischemia as measured by exercise bicycle echocardiogram stress testing.

We hope that this study, the first of its kind in the USA using the CS Reducer as potential therapy for angina with no obstructive CAD (ANOCA) will address the therapeutic potential of CS narrowing for the treatment of CMD, an important unmet clinical need, and generate preliminary data for larger randomized phase 2 and 3 trials.

Study protocol

1- Introduction

This document is a human research study protocol. This study will be carried out in accordance with the applicable United States government regulations and Mayo Clinic research policies and procedures.

2- Background

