Figure 2: A) Improvement in Canadian Cardiovascular Society (CCS) class, Seattle Angina Questionnaire (SAQ) score, and 6 minute walk test (6MWT) at 4 months post CS Reducer implantation. B) Improved myocardial perfusion reserve index in a subgroup of patients. Adapted from Giannini F et al., JACC Cardiovascular Interventions ³².

More supportive data for the concept that increased CS pressure might improve microvascular function can be found in a very recent case presented by Tommaso Gori ³⁹ of a 61 year old man who presented with severe (CCS class 4) angina, non-obstructive CAD and elevated IMR. This patient was treated with Reducer implantation with consequent resolution of angina and dramatic reduction in IMR. Also, CS pressure elevation using pressure-controlled

intermittent CS occlusion (PISCO) in patients presenting with first anterior STEMI, resulted in improves microvascular function (reduction in IMR values) as well as reduction of infarct size (OxAMI-PISCO study)³³.

Safety and Procedural Success of CS Reducer System and Implantation Procedure

The safety and procedural success of CS Reducer implantation has been demonstrated in one randomized clinical trial and numerous observational studies done in Europe and Canada^{36, 37, 40, 41}. To date, no feasibility and efficacy studies have been done in the United States.

Potential complications of the procedure include dissection or perforation of the CS and device migration. However, as demonstrated in previous studies (COSIRA, n=52 and REDUCER-I, n=204) and non-published post-marketing commercial use in more than 1800 patients worldwide, no cases of mortality has been recorded and the rates of aforementioned complications, including myocardial infarction or permanent damage related to the device or procedure such as perforation, are very low (Table 1). Moreover, implantation procedure has very high success rates. The largest multicenter Italian registry reports 98.6% (n=139) procedural success with 2 patients (1.4%) failing due to unfavorable anatomy of the coronary sinus⁴¹. Summary of technical success data of CS Reducer implantation procedure from four previous studies is summarized in Table 2.

Table 1: Safety Data of CS Reducer System and Implantation Procedure³

Potential Complications (REDIFU-002 Reducer IFUCE Mark REV K)	Pre-Market Event Rate (COSIRA) N=52 n(%)	Post-Market Event Rate (REDUCER-I) N=204 n(%)	Post-Market Event Rate (Commercial Use) N=1840 n(%)

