² *One subject experienced a migration post-implantation. The Reducer was noted to have moved during insertion but was inflated. As a result, the position of the deployed Reducer device was more proximal than desired. The dislodged Reducer then migrated and a 2nd Reducer was implanted without complications*

³ *Seven subjects were not implanted – 2 for CS dissection, 2 for tortuous anatomy, 1 for CS too small, 1 for inability to advance the guiding catheter, and 1 for movement of the Reducer while retracting the guidewire*

Accordingly, in this Phase-1 study we aim to evaluate the feasibility of CS Reducer implantation and its efficacy on invasively assessed microvascular function in ANOCA patients with CMD.

4- Study Hypothesis

In patients with ANOCA and invasive evidence of CMD, CS Reducer implantation is safe and will improve microvascular function as measured by CFR and HMR.

5- Aims

- 5.1 To evaluate the potential efficacy of CS Reducer implantation in ANOCA patients with CMD on microvascular function using invasive CFR and HMR assessments
- 5.2 To evaluate the potential efficacy of CS Reducer implantation in ANOCA patients with CMD on angina severity and frequency as assessed by CCS angina class and short-acting nitrates use, ischemia and exercise capacity as assessed by exercise bike echocardiographic stress test (EBEST), and quality of life as assessed by SAQ score.
- 5.3 To evaluate the potential efficacy of CS Reducer on left ventricular diastolic function and filling pressures as assessed by transthoracic echocardiographic parameters at peak exercise
- 5.4 To confirm the safety and feasibility of CS Reducer implantation patients with ANOCA and invasively documented CMD.
- 5.5 A successful demonstration in the proposed trial that CS Reducer implantation can be beneficial to patients with CMD will significantly advance the field of research aimed at FDA approval of the CS Reducer for treatment of ANOCA patients with CMD and opening the door to commercialization of CS Reducer for treatment of CMD, which is a critical unmet clinical need. If successful, the next stage of investigation will be the conduct of one or more pivotal registration studies to support FDA approval, and the proposed trial will provide information necessary to design these studies.

6- Study design

6.1 General Study Design:

- Prospective, single center, open label, single arm, clinical trial
- Number of participants: 30 subjects
- Duration of study: 4 months

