6.3 Secondary Endpoints

- Change in CCS angina class
- Change in the score of all 5 domains of the Seattle Angina Questionnaire for assessing quality of life
- Change in the consumption and frequency of short acting nitrates (spray or sublingual tablets)
- Change in EBEST parameters at 4 months compared with baseline (total exercise duration, time to 1 mm ST segment depression, evidence of ischemia, peak exercise stage, peak exercise diastolic function and filling pressures as measured by echocardiographic E/e', and exercise-induced symptoms)

- Procedural-related Major Adverse Cardiac Events (MACE) defined as: death, myocardial infarction, perforation of the CS, CS total occlusion, or need for urgent dilatation of the Reducer within 4 months of follow-up

7- Study Population:

Patients with chronic refractory angina (CCS class II-IV), no obstructive CAD (<50% stenosis in epicardial vessels and/or iFR>0.89 or FFR>0.8 in vessels with 50 to 70% stenosis), and documented CMD (CFR≤2.5 and/or HMR≥2.5) & or coronary blood flow (CBF) response to acetylcholine ≤ 50%. on clinically indicated coronary angiography and invasive coronary reactivity testing which uses Adenosine, Acetylcholine & Nitroglycerin as standard clinical practice

7.1 Inclusion Criteria:

- Age ≥ 18
- Able to provide written informed consent and willing to participate in all required study follow-up assessments
- Symptomatic CAD with refractory angina defined as CCS class II to IV, despite optimal tolerated medical therapy for more than 3 months.
- Abnormal coronary microvascular function indices: CFR≤2.5 and/or HMR≥2.5 & or coronary blood flow (CBF) response to acetylcholine ≤ 50%.

7.2 Exclusion Criteria:

- Recent (within 3 months) acute coronary syndrome
- Recent (within 6 months) percutaneous coronary intervention revascularization by stent
- Patients with prior coronary artery bypass surgery

- Unstable angina (recent onset angina, crescendo angina, or rest angina with ECG changes) during the last 30 days
- Subjects in cardiogenic shock (systolic pressure < 80mm/Hg, on vasopressors or intraaortic counter pulsation) at the time of consenting. Subjects who recover from cardiogenic shock by the time of consenting are eligible.
- Obstructive CAD on coronary angiography (>70% stenosis or 50-70% stenosis with $iFR \leq 0.89$ or $FFR \leq 0.8$ in epicardial artery)
- Inability to perform invasive coronary flow evaluation and/or measure CFR and HMR in the LAD
- Severe valvular heart disease

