The first six patients will be sequentially enrolled, and subsequent enrollment will be held until one-month follow-up. Provided there are no safety concerns at this time, enrollment will continue. Staggered enrollment will help ensure that subsequent patients are not enrolled until there is adequate follow-up and safety of initial patients. The patients for this study will be recruited through the outpatient clinics in the Department of cardiology, including the Chest Pain and Coronary Physiology Clinic and the Coronary Artery Disease Clinic at Mayo Clinic. There have been over 35,000 patients seen in the Cardiovascular Division at Mayo Clinic yearly. There are over 6,000 cardiac catheterizations performed yearly in the cardiac catheterization lab. As a part of our clinical practice, patients with angina referred to the catheterization laboratory for a clinically indicated coronary angiography and found to have non-obstructive CAD are undergoing a comprehensive coronary reactivity testing including assessment of microvascular function with CFR and HMR. Typically, 8-10 patients per month undergo this comprehensive coronary physiology study. This will be mediated through referring physicians. Patients that meet inclusion and exclusion criteria will be considered for recruitment in the study.

7.4 When and How to Withdraw Subjects:

Subjects will be withdrawn from the study prior to completion of all study related procedures if 1 of 5 consecutive patients have serious adverse safety events.

7.5 Data Collection and Follow-up for Withdrawn Subjects:

Even though a subject has withdrawn from the study, it may be important to collect some follow-up or survival data on such subjects throughout the protocol defined follow-up period. Such data is important to the integrity of the final study analysis since early withdrawal could be related to the safety profile of the study device and/or implantation procedure. If a subject withdraws consent to participate in the study, for subject safety reasons, we will make attempts to obtain permission to collect follow up information whenever possible.

[figure not shown]

Figure 3: Flow chart of the study design. CAD: coronary artery disease; CMD: coronary microvascular dysfunction; CRT: coronary reactivity testing; CFR: coronary flow reserve; HMR: Hyperemic microvascular resistance; CCS: Canadian cardiovascular society; SAQ: Seattle angina questionnaire; EBEST: Exercise bike echocardiographic stress test.

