11.8 Schedule of Study Procedures and Assessments

Study Procedure/ Assessment	Screening	Enrolment/ Pre-Implant	Implant Day	Post-Implant			
Days	-30	-5 to -1	0	30	60	90	120

Windows				± 4	±7	±7	±14
Eligibility criteria	X						
Informed consent	X						
Medical history	X						
Vital signs	X	X	X				X
12-lead ECG	X	X	X				X
Standard laboratory tests including hematology, blood chemistry, liver function tests, CRP and creatinine, urinalysis.		X*					X
EBEST		X					X
CS Reducer Implant			X				
CCS Angina Class		X		X	X	X	X
SAQ		X		X	X	X	X
Coronary angiography to measure CFR and HMR							X
Physical exam	X						
Limited physical exam			X				
Adverse events	X	X	X	X	X	X	X

Concomitant medications	X						
-------------------------	----------	----------	----------	----------	----------	----------	----------

- a. CS Reducer will be implanted in the coronary sinus through right (preferably, or left internal jugular venous access)
- b. The patient will receive a phone call from the study coordinator to collect information on adverse events, angina class, SAQ, and concomitant medications.
- c. Vital signs will be measured prior to implant and every 8 hours until discharge
 - * Standard pre-procedural laboratory tests including hematology and blood chemistry including creatinine. Liver function tests, CRP, and urinalysis only at Day 120.

12- Statistical Plan

The effect of the CS Reducer implantation on microvascular function will be evaluated by the change in measured CFR and HMR at 4 months follow-up compared to baseline pre-CS Reducer implantation. Statistical analysis of the absolute and percent change in CFR and HMR measurements at follow-up will be done. Analysis of the delta change in CFR and HMR will also be performed. Change in angina intensity and frequency, and quality of life, will be evaluated by analyzing the change in CCS angina class, SAQ score in all five domains, and antianginals need and frequency from baseline to follow-up. Change in functional capacity will be evaluated as the change in baseline to follow-up EBEST total exercise duration, peak exercise stage, exercise-induced symptoms, and ischemic ECG and echocardiographic findings. Change in diastolic function and filling pressures will be evaluated as baseline to follow-up change in resting and peak exercise echocardiographic E/e' ratio.

All-completed population: Only subjects who completed ALL study related procedures and follow-up will be included in analysis.

13- Safety and Adverse Events

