13.4 Adverse Event Reporting Period

Serious adverse events should be reported using the Serious Adverse Event Report Form within 24 hours of study personnel becoming aware of an event. This data must be entered into the electronic capture system within 24 hours as well.

If serious adverse event results in death or is considered to be related to the study device, then the medical monitor must be contacted immediately.

The follow-up period is defined as 4 months following CS Reducer implant. This is the study period during which adverse events must be reported.

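### Restricting all analysis to patients who completed every procedure removes deaths and failed implants from the MACE and procedural-success results and can discard valid CFR/HMR pairs

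*Combined protocol and SAP*

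**What the plan says.** The last sentence of Section 12 (Statistical Plan) names an all-completed population and states: "Only subjects who completed ALL study related procedures and follow-up will be included in analysis". This is the only analysis set in the document. There is no missing-data rule.

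Several other places bear on it:

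- Section 6.3 includes this secondary endpoint, counted over the 4-month follow-up: "Procedural-related Major Adverse Cardiac Events (MACE) defined as: death, myocardial infarction, perforation of the CS, CS total occlusion, or need for urgent dilatation".
- The Project Summary says "Additional data will be collected on the adverse events and procedural success of the Reducer implantation procedure". Aim 5.4 is to confirm safety and feasibility, and Aim 5.5 says the trial will inform the design of pivotal studies.
- Section 7.4 provides for withdrawal in these terms: "withdrawn from the study prior to completion of all study related procedures if 1 of 5 consecutive patients have serious adverse safety events". It does not say which subjects.
- Section 7.5, on follow-up data from withdrawn subjects, gives a reason that concerns the device and procedure: "Such data is important to the integrity of the final study analysis since early withdrawal could be related to the safety profile".
- Sections 11.3 to 11.8 schedule the implant, phone calls at Days 30, 60 and 90, and ten listed items at Day 120. The repeat CFR/HMR study is one of those ten.
- Section 13.4: "The follow-up period is defined as 4 months following CS Reducer implant".

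**The concern.** A completer set is defined by what happens after treatment starts. For safety and feasibility outcomes, the events of interest are themselves reasons for not completing. A patient who dies before Day 120 cannot have the Day 120 assessments. A patient in whom the device cannot be placed has not had the implant. Neither can be counted, although death is a MACE component and failure to implant is what a procedural-success figure is meant to measure. Non-fatal MACE in patients who go on to complete everything still counts, but it is missed whenever the event prevents completion.

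Section 7.4 makes the link closer: it ties serious safety events to withdrawal before all procedures are complete, which is the condition Section 12 uses to exclude. Section 7.5 points the other way, saying that data from withdrawn subjects matter to the final analysis.

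The primary endpoint is affected too. A patient with valid baseline and 4-month CFR and HMR is dropped for missing a phone call, a laboratory test or the exercise echocardiogram, none of which is needed to compute the change.

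**Working it through.** **Reading the rule against the schedule**

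| Patient | Completed every procedure and follow-up? | Result under Section 12 |
|---|---|---|
| Dies before Day 120 | No | Death not counted in MACE |
| Implant attempted, device not placed | No | Failure not counted in procedural success |
| Non-fatal MACE, then completes everything | Yes | Counted |
| Non-fatal MACE that prevents completion | No | Not counted |
| Both CFR/HMR studies done, one phone call missed | No | Valid primary-endpoint pair discarded |

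The Day 120 visit has a window of ±14 days, so a patient could have every assessment at Day 106 and die soon after. That patient has still not completed follow-up, because Section 13.4 sets it at 4 months from implant.

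**Inputs for failed implants**

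The plan gives no sample-size or attrition calculation to reproduce. The failure rates come from Section 3.

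- Italian registry, Section 3 text: "procedural success with 2 patients (1.4%) failing due to unfavorable anatomy of the coronary sinus".
- REDUCER-I overall, Table 2: 204/211 implanted, so 7/211 = 3.32% not implanted. (204/211 is 96.68%; the table prints 96.6. This does not matter here.)
- COSIRA treatment arm, Table 2: 50/52 = 96.2% as printed, so 2/52 = 3.85% not implanted.
- The first-in-man series (14/15) is not used, because its one failure received a second Reducer.

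Table 2, footnote 3, lists among the seven REDUCER-I failures "2 for CS dissection, 2 for tortuous anatomy, 1 for CS too small". The protocol excludes abnormal coronary sinus anatomy and diameters outside a stated range. Removing the three failures for tortuosity or small size leaves 4/211 = 1.90%.

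**Expected failures and chance of at least one in 30 attempts**

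Expected = 30p; P(at least one) = 1 − (1 − p)^30.

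| Source | p | Expected | P(at least one) |
|---|---|---|---|
| Italian registry | 1.4% | 0.42 | 34.5% |
| REDUCER-I | 7/211 = 3.32% | 1.00 | 63.7% |
| COSIRA | 2/52 = 3.85% | 1.15 | 69.2% |
| REDUCER-I, three anatomical failures removed | 4/211 = 1.90% | 0.57 | 43.7% |

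**Effect on the reported figures (exact Clopper-Pearson 95% intervals)**

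One failed implant, all other patients complete:

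- All attempted: 29/30 = 96.7% (82.8% to 99.9%).
- Section 12 as written: 29/29 = 100% (88.1% to 100%).

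One failed implant and one MACE death before Day 120 (an assumed example):

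- All attempted: MACE 1/30 = 3.3% (0.1% to 17.2%); success 29/30 = 96.7%.
- Section 12 as written: MACE 0/28 = 0% (upper limit 12.3%); success 28/28 = 100%.

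**Loss of CFR/HMR pairs**

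Each pair discarded for another missed item costs 1/30 = 3.3% of the sample. The documents give no missing-item rate, so no total can be derived. As an illustration only, assume that the three phone calls and the Day 120 exercise test are each missed independently with probability m, and that all 30 patients have both invasive studies. Pairs discarded = 30 × [1 − (1 − m)^4]: 2.3 at m = 2%, 5.6 at m = 5% and 10.3 at m = 10%.

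**The case against.** The strongest reply is that Section 12 was meant for efficacy only. The paragraph before the sentence lists CFR/HMR, CCS, SAQ, antianginal use, exercise and diastolic measures, and names neither MACE nor procedural success. Safety has its own Section 13, which collects events from consent to the 4-month visit in every subject. That may well be the intention, but the sentence does not say so. If it is right, a declared secondary endpoint has no analysis population at all, and the rule still discards valid primary-endpoint pairs. Section 13 sets reporting duties; it sets no denominator for a MACE or success rate.

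Other objections stand in part:

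- Procedural success is data to be collected, not a listed endpoint. It still bears on the feasibility aim.
- Deaths should be rare. Section 3 reports none in COSIRA, REDUCER-I or commercial use. With 0 in 52 + 204 + 1840 = 2096, the rule-of-three upper limit is 3/2096 = 0.14%, or about 0.04 deaths in 30, if those data apply to this population.
- The failed-implant rates may be too high here. Both registry failures were anatomical, so the adjustment made for REDUCER-I would take that rate to zero, and the two COSIRA failures may or may not have been anatomical. Against this, the listed screening and pre-implant procedures include no coronary sinus imaging, so unsuitable anatomy may first be seen at the implant procedure.
- Section 7.4 is itself unclear about who is withdrawn, so its contribution cannot be sized.

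**Conclusion.** The concern holds and should be corrected before analysis. As written, the rule fixes the death component of MACE at zero and implant success among analysed patients at 100%, whatever happens in the trial. This follows from the wording and needs no assumption about rates.

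The practical size rests mainly on failed implants. Applying the cited failure rates unadjusted gives 0.4 to 1.2 expected in 30 and a 34% to 69% chance of at least one. These figures could be lower here because of the anatomical exclusions. Deaths are unlikely on the cited experience, but the rule would hide any that occurred. The loss of CFR/HMR pairs is certain in kind and unknown in amount, and the documents do not allow the size or direction of any efficacy bias to be derived.

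The distortion is in the analysed results. Adverse-event recording, regulatory reporting and DSMB review would still see these patients. It matters because the study is meant to establish safety and feasibility and to supply inputs for later trials.

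**What to change.** Replace the sentence in Section 12 with endpoint-specific sets:

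1. **MACE and procedural success:** all patients in whom implantation was attempted, with the start of an attempt defined in advance. Count failed implants as failures, give exact 95% confidence intervals, and count events from the attempt in patients who are not implanted.
2. **CFR and HMR:** all implanted patients with both invasive measurements, whatever else is missing. Report the number without a repeat measurement and the reasons. This recovers pairs lost to other missed items; it does not remove bias from patients who do not return for the repeat study.
3. **CCS, SAQ and exercise echocardiography:** all implanted patients with data for the endpoint concerned.
4. **All-completed set:** a sensitivity analysis only.

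Reconcile Section 12 with Sections 7.4 and 7.5, so that it is clear which subjects are withdrawn and how their data enter the analysis.

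The cost is mainly wording. One addition is needed: Section 13.4 starts follow-up at the implant, so a short follow-up rule is required for patients attempted but not implanted. Reported safety and success rates may look less favourable.
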